# 9.1.2.2 Dose Proportionality

Dose proportionality will be analyzed using a power model. The natural log-transformed (ln) parameters ( $C_{max}$  and AUCs: AUC0-t and AUC0-∞) will be fit to a linear model estimating the effect of ln(dose) (Gough 1995). The empirical relationship between a PK parameter and dose is in the following equation:

$$PK = e^{\alpha} * (dose)^{\beta}$$

Where PK represents the PK parameter AUCs and  $C_{max}$ . For analysis, this equation is natural log-transformed, obtaining the equation below:

$$InPK = \alpha + \beta * In(dose)$$

The slope  $\beta$  measures the dose-proportionality between dose and the PK parameter.

The confidence interval criteria for assessment of dose proportionality from Smith et al. (2000) will be used to test for dose proportionality. The *a priori* acceptance range for the slope, according to Smith, is given by:

$$1 + In(0.8)/In(r) < \beta < 1 + In(1.25)/In(r)$$

Where 1.25 and 0.8 are the critical *a priori* values suggested by regulatory authorities for any bioequivalence problem after a data log transformation, and r is the ratio of the largest dose to the smallest dose. Dose proportionality can be claimed if the 90% confidence interval for the slope is entirely contained within this *a priori* range.

Dose proportionality will also be explored graphically: regression/scatter plot in the In-In scale for the power analysis.

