The sample size of this study is not based on statistical considerations;

Statistical Analyses

A formal statistical analysis plan will be developed and finalized prior to unblinding the data. This plan will define the healthy population for analysis, outline all data handling conventions, and specify all statistical methods to be used for analysis of the data.

Safety and tolerability results from this study will be assessed using summary statistics by cohort (e.g., n, mean, median, minimum, maximum, for continuous endpoints; n and % for binary and categorical endpoints). All placebo subjects from the different cohorts will be combined into a single group for summary purposes.

PK parameters will be summarized by cohort using descriptive statistics (e.g., n, arithmetic means, geometric means, standard deviation, % coefficient of variation, median, minimum, and maximum). Figures will be created to display mean and individual subject PMN310 concentration time curves in serum on both a linear and logarithmic scale. Dose proportionality will be assessed using linear regression, or another acceptable approach.

The outcomes of this first in human study will be used for dose selection and preliminary statistical power calculations for subsequent studies in patients with AD.

TABLE OF CONTENTS

PROTO	COL SIGNATURE PAGE	2
PROTO	COL SYNOPSIS	3
1.	INTRODUCTION	16
1.1.	Alzheimer's Disease	16
1.1.1.	Monoclonal Antibody Therapy in Alzheimer's Disease	16
1.2.	PMN310	17
1.2.1.	Nonclinical Studies	17
1.3.	Study Rationale	19
1.4.	Rationale for Dose Selection	19
1.5.	Benefit-Risk Assessment	20
2.	STUDY OBJECTIVES AND ENDPOINTS	21
2.1.	Study Objectives	21
2.1.1.	Primary Objectives	21
2.1.2.	Secondary Objectives	21
2.1.3.	Exploratory Objectives	21
2.2.	Study Endpoints	21
2.2.1.	Primary Endpoints	21
2.2.2.	Secondary Endpoints	21
2.2.3.	Exploratory Endpoints	21
3.	STUDY DESIGN	22
3.1.	Design Characteristics	22
3.1.1.	Dose Escalation Rules	22
3.1.2.	Safety Review Committee	24
4.	STUDY POPULATION	25
4.1.	Inclusion Criteria	25
4.2.	Exclusion Criteria	26
5.	STUDY TREATMENTS	28
5.1.	Identification and Description of Study Drug	28
5.1.1.	PMN310	28
5.1.2.	Placebo	28
5.2.	Study Drug Preparation and Administration	28

5.2.1.	PMN310	28
5.2.2.	Placebo	28
5.3.	Randomization and Blinding	28
5.4.	Unblinding for an Individual Subject	29
5.5.	Dose Escalation/Stopping Rules	29
5.6.	Storage, Handling, and Accountability of Study Drug	29
5.7.	Prior and Concomitant Therapy	30

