5.2. Study Drug Preparation and Administration

5.2.1. PMN310

Study medication will be prepared at the study clinic by an unblinded pharmacist (or designee) based on an individual subject's randomization or assigned treatment. Once prepared, blinded IV drug for infusion will be dispensed to staff who will administer study drug. Specific instructions for preparation and administration of study medication will be provided in the Pharmacy Manual.

PMN310 will be administered as a single IV infusion over 60 minutes in 0.9% NaCl, adjusted to a total volume of 100 mL, followed by a 15 minute 0.9% NaCl flush. The complete infusion will consist of the IV infusion and the flush following the IV infusion.

The following dose level cohorts are planned to be evaluated: 175 mg (starting dose level), 350 mg, 700 mg, 1400 mg, and 2800 mg (optional cohort). The rationale for selecting these dose levels is provided in Section 1.4.

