9.4.2. Pharmacokinetic Analysis

The PK population will be used for the PK analysis. PMN310 serum concentration data will be listed by cohort, subject, and visit/sampling time point. Descriptive summary statistics will be provided by cohort and visit/sampling time point. Summary statistics will include mean (arithmetic and geometric), standard deviation (SD), coefficient of variation (CV) (arithmetic and geometric), median, minimum, and maximum. Concentrations below lower limit of quantitation will be treated as zero in summary statistics.

On the basis of PMN310 concentration -time data, the following PK parameters will be estimated using standard noncompartmental methods using Phoenix WinNonlin Version 8.0 or higher:

Page 52

- AUC_{0-t}, calculated by using the linear-log trapezoidal rule: linear trapezoidal rule up to maximum concentration, and then a log trapezoidal rule for the remainder of the curve, where t corresponds to the last measurable time point
- $AUC_{0-\infty} = AUC_{0-t} + C_t/\lambda_z$, where C_t is the last measurable serum PMN310 concentration and λ_z is the terminal elimination rate constant calculated by using loglinear regression of the terminal elimination phase of the serum concentration versus time curve
- C_{max} of PMN310 from the observed PMN310 concentration-time data
- T_{max} of PMN310 from the observed PMN310 concentration-time data
- $t_{1/2}$ calculated as follows: $ln(2)/\lambda_z$
- Vd = volume of distribution during the terminal phase
- CL = total body clearance
- $\lambda z = \text{terminal elimination rate constant}$

PK parameters will be summarized by cohort using descriptive statistics (e.g., n, arithmetic means, geometric means, SD, %CV, median, minimum, and maximum). Figures will be created to display mean and individual subject PMN310 concentration time curves in serum on both a linear and logarithmic scale.

Dose proportionality of PMN310 will be assessed using a power model. The PK parameters to be analyzed are C_{max} and AUC_{last}. A natural logarithmic transformation will be applied for the power model, which implies to a general linear model to the log transformed PK parameter with a fixed continuous log-dose effect (i.e. log (PK parameter) = $log(\alpha) + \beta log(Dose) + \epsilon$). An assessment of the relationship between the doses of PMN310 and the PK parameters will be obtained from the estimate of the slope and the corresponding 90% confidence interval.

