#### 5.2 Dose Levels

Table 2 summarizes the dose level cohorts that are planned to be evaluated.

Table 2 Planned Study Drug Dose Levels

Cohort	Expected Number of Evaluable Subjects	PMN310 Dose Level
1	6 PMN310, 2 placebo	175 mg (starting dose level)
2	6 PMN310, 2 placebo	350 mg
3	6 PMN310, 2 placebo	700 mg
4	6 PMN310, 2 placebo	1400 mg
5	6 PMN310, 2 placebo	2800 mg (optional cohort)

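### The rule for claiming dose proportionality uses the slope interval alone and has no curvature check, so roughly symmetric curvature outside the SAP's own 0.80–1.25 margin can pass when between-subject variability is low

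*SAP*

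**What the plan says.** SAP 9.1.2.2 covers Cmax, AUC0-t and AUC0-∞. The natural-log parameters "will be fit to a linear model estimating the effect of ln(dose) (Gough 1995"), giving a single slope β. The acceptance range for β is built from 0.8, 1.25 and r, where "r is the ratio of the largest dose to the smallest dose". The decision rule is "Dose proportionality can be claimed if the 90% confidence interval for the slope is entirely contained within this" range. The section then adds an exploratory regression/scatter plot on the ln-ln scale, with no criterion attached.

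Protocol 9.4.2 plans the same power model for Cmax and AUClast, without an acceptance range: "An assessment of the relationship between the doses of PMN310 and the PK parameters will be obtained from the estimate of the slope" and its 90% confidence interval.

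Protocol 5.2.1 lists the dose cohorts as "175 mg (starting dose level), 350 mg, 700 mg, 1400 mg, and 2800 mg (optional cohort"). SAP 5.2 and 6.1 give six PMN310 subjects per cohort. The protocol synopsis allows intermediate doses in place of planned ones.

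SAP 9.1.1 summarises the serum PK parameters by dose level, with geometric mean and geometric CV% for all but the time-related parameters and the extrapolated AUC percentage. Clearance is among the parameters in SAP 9.1.2.1.

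On use of the results, the synopsis says "The outcomes of this first in human study will be used for dose selection" in later studies.

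**The concern.** A straight-line slope answers one question: does exposure rise, on average over the range, in step with dose? It does not show whether the line fits. With equally spaced ln-doses and equal numbers per dose, a curvature term is orthogonal to the slope. Exposure that is relatively low at both ends, or high at both ends, then leaves β centred on 1.

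The rule can therefore return a claim of proportionality over a 16-fold range for a drug whose end-to-middle dose-normalised ratio lies outside the margin from which the rule is built. A reader of that claim would expect the same fold-rise in exposure for each fold-rise in dose, when the lower and upper halves of the range differ. Five dose levels with six subjects each hold information on this, and the formal criterion does not use it.

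**Working it through.** The documents state no power, CV or numeric slope limits for this analysis, so there is no plan figure to reproduce.

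**Inputs.** From the documents: doses 175 to 2800 mg in doublings; six PMN310 subjects per dose; margins 0.8 and 1.25; 90% CI. Assumed: log-normal data with the same between-subject CV at every dose, 10% to 25%.

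**Limits for β.** 1 + ln(0.8)/ln(r) to 1 + ln(1.25)/ln(r).
- Five cohorts, r = 2800/175 = 16: 0.9195 to 1.0805.
- Four cohorts, r = 1400/175 = 8: 0.8927 to 1.1073.

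**Expected slope.** In units of ln 2 the five centred doses are −2, −1, 0, 1, 2. Let f be the true dose-normalised exposure relative to 700 mg. Then β = 1 + Σ(score × ln f)/(10 × ln 2).
- Symmetric, f = 0.75, 0.93, 1, 0.93, 0.75: the terms cancel and β = 1.000.
- Lowest dose only, f = 0.75, 1, 1, 1, 1: β = 1 + (2 × 0.2877)/6.931 = 1.083, above the upper limit.
- Monotone, f = 0.75, 0.85, 0.95, 1, 1: β = 1.107, also above it.

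**What the symmetric case means.** True exposure rises by 4/0.75 = 5.3 from 175 to 700 mg and by 4 × 0.75 = 3.0 from 700 to 2800 mg. A line with slope 1 gives 4.0 for both.

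**Width of the interval at CV 20%, five cohorts.** Sxx = 6 × 10 × (ln 2)² = 28.83; residual variance ln(1 + 0.20²) = 0.0392; t with 28 df = 1.701.
- Proportional drug: half-width 1.701 × √(0.0392/28.83) = 0.063, so 0.937 to 1.063.
- Symmetric drug: the misfit adds a sum of squares of 0.433, so the residual variance becomes 0.0392 + 0.433/28 = 0.0547. The half-width is 0.074, so 0.926 to 1.074.

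Curvature widens the interval, but the expected interval still lies inside the limits.

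**Probability that the rule allows a claim** (simulation; repeat runs agree to about one percentage point):

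| True shape | CV 10% | 15% | 20% | 25% |
|---|---|---|---|---|
| Five cohorts, proportional | 99% | 77% | 37% | 10% |
| Five cohorts, 0.75/0.93/1/0.93/0.75 | 88% | 49% | 17% | 3% |
| Five cohorts, 0.75/0.95/1/0.95/0.85 | 49% | 31% | 15% | 4% |
| Four cohorts, proportional | 98% | 68% | 28% | 6% |
| Four cohorts, 0.75/1/1/0.75 | 65% | 25% | 7% | 1% |

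A 25% fall at one end only passes in at most about 3% of trials at any CV tried, and the monotone shape in at most about 1%.

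**Can the planned data show it?** A quadratic ln(dose) term whose 90% CI excludes 0 picks up the five-cohort symmetric shape in more than 99.9%, 99.7%, 95% and 84% of trials at the four CVs.

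**The case against.** The slope-interval method is a cited, recognised approach. Dose proportionality is not a listed endpoint, the study is not sized statistically, and SAP 6.6 plans no formal hypothesis testing. The rule says that proportionality can be claimed, not that it must be. An ln-ln plot is planned in the same section.

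A reader might infer that no dose-normalised look is planned. That would be wrong for AUC0-∞. After a single IV dose CL = dose/AUC0-∞, so geometric mean CL by dose is the reciprocal of dose-normalised AUC0-∞. The symmetric drug would show CL about 1/0.75 = 1.33 times as high at the end doses as at 700 mg. Cmax and AUC0-t are also tabulated by dose, though not dose-normalised. What remains is that these displays carry no ratio CI and have no stated role in the claim.

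A reader might also infer that the analysis cannot see curvature at all. It can see most of it: one-ended and monotone falls shift the slope, and symmetric curvature widens the interval (at CV 20%, claims drop from 37% to 17%). Nothing in the documents suggests that PMN310 exposure would be hump- or U-shaped.

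The synopsis ties dose selection to the study's outcomes as a whole, not to the slope verdict, so the documents do not support saying that later doses would be chosen on a wrong claim.

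Finally, if intermediate doses replace planned ones, exact orthogonality is lost. Purely as arithmetic, 175, 350, 700, 1000 and 1400 mg with 25% falls at both ends gives β = 1.029. That still passes in 12% of trials at CV 20%, so uneven spacing weakens the point without removing it.

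**Conclusion.** The point holds in a limited form. The formal criterion has no curvature or lack-of-fit check. On the planned grid, roughly symmetric curvature with an end-to-middle ratio of 0.75 can pass a rule built on 0.80–1.25. The risk is material at a CV of about 20% or less and small at 25% or more, where a truly proportional drug rarely passes either (10% with five cohorts). So a wrong claim is most likely in the settings where the rule yields claims at all.

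The sizes rest on an assumed CV, log-normal data with equal variance, six evaluable subjects per dose, and shapes chosen to illustrate the gap. Severity is minor to moderate: PK is secondary, the needed CV is not in the documents, and other planned displays could reveal the problem to an attentive reader.

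**What to change.** In SAP 9.1.2.2, for Cmax, AUC0-t and AUC0-∞:

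1. Also fit a centred quadratic term, γ × (ln(dose) − mean ln(dose))², and report γ with its 90% CI as a lack-of-fit check.
2. Tabulate dose-normalised geometric mean ratios to one pre-named reference dose, with 90% CIs.
3. State that an overall claim is made only after the slope has been read together with these results and the planned plot. Where they show a departure of relevant size against 0.80–1.25, describe proportionality dose by dose.

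Do not make non-significance of γ an automatic gate. For a slight dip (0.90/0.97/1/0.97/0.90, inside the margin), requiring the CI for γ to include 0 would cut claims from 99% to 25% at CV 10% and from 72% to 40% at CV 15%. It would penalise precise data.

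The ratio table should not become a pass/fail rule either. With six per dose and a pooled variance (25 df, t = 1.708), the 90% CI around a true ratio of 1 at CV 20% (log-scale SD 0.198) is exp(±1.708 × 0.198 × √(2/6)), about 0.82 to 1.22. At CV 25% (SD 0.246) it is about 0.78 to 1.27, already wider than the margin.

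The cost is a few lines of SAP text and one extra model and table per parameter on data already collected. The downside is somewhat fewer unqualified claims of proportionality.

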## 9.2 Cerebrospinal Fluid (CSF) Pharmacokinetic Analyses

All CSF analyses will be conducted using the Evaluable population.

Descriptive summaries of CSF concentration time data by nominal time point and cohort/dose level will be provided. Summary statistics for PMN310 concentration-time data will include the

CONFIDENTIAL Page 29 of 32

following: n (number of participants with non-missing values), mean, SD, arithmetic coefficient of variation (CV (%)), median, minimum, maximum, geometric mean and 90% confidence interval (CI), geometric CV (%), and the number (percentage) of samples are BLQ. All concentration-time data and relevant summary statistics will be reported to the same number of significant figures as displayed in the bioanalytical data. For calculation of summary statistics, concentration values that are BLQ will be set to 0 for all BLQ concentrations. Nominal sampling time points relative to the start of dosing will be used for tabulation by time point for summaries of concentration-time data. If >25% of values at a time point within a treatment level are missing or BLQ, no summary statistics are presented.

No CSF parameters will be estimated apart from CSF:serum PMN310 ratio.

CSF PMN310 concentration data and serum PMN310 concentration data will be compared by cohort/dose level using summary statistics for nominal time points that have both data points available. Mean (±SD) values may also be plotted, as data permits.

All CSF data will be presented by timepoint in a by-subject listing.

#### 10 EXPLORATORY ENDPOINT ANALYSES

## 10.1 Immunogenicity

All immunogenicity analyses will be conducted using the Safety population.

Immunogenicity results will be summarized descriptively by PMN310 dose level and visit for the number and percentage of subjects who develop detectable levels of anti-PMN310 antibodies (ADA). ADA status will be treated as categorical data (positive and negative) and summarized descriptively by visit. In addition, a subject will be considered positive for PMN310-induced immunogenicity if the subject has at least one confirmed positive ADA response after dosing in the study.

Titer data will also be summarized descriptively for continuous data (n, mean, standard deviation, median, minimum, maximum, geometric mean, and geometric CV%) by PMN310 dose level and visit for the observed value.

Individual serum and/or CSF concentrations of PMN310 and mean (±SD) PMN310 concentrations versus time may be presented separately in ADA positive and negative subjects. Possible correlation between PK concentrations and any post-dose ADA responses may be evaluated using graphical presentation to identify a potential impact of anti-PMN310 antibodies on drug exposure. The ADA status is considered in a cumulative manner at each time point (i.e., if a subject had a positive sample at any time point of assessment visit that subject would be counted as positive throughout the study).

All immunogenicity data will be presented by timepoint in a by-subject listing.

CONFIDENTIAL Page 30 of 32

Study PMN310-101 PMN310 ProMIS Neurosciences, Inc SAP Final v1.0

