# 6.2 Analysis Populations

There will be four (4) analysis populations defined for this study. These analysis populations may be further refined, and additional analysis populations may be defined, for example, for the analysis of data for a specific assay, based on sample availability and suitability. Any changes will be summarized in the Clinical Study Report (CSR).

- The Safety population will include all subjects who receive study drug. Subjects will be analyzed as treated.
- The PK population will include all subjects who receive study drug and have at least 1 post-dose quantifiable concentration for PK analysis. The PK population will be used for the serum PMN310 concentration analyses. Subjects will be analyzed as treated.
- The Evaluable population will include all subjects who complete at least 1 post-dose lumbar puncture (LP). The Evaluable population will be used for the cerebrospinal fluid (CSF) PMN310 concentrations. Residual and unused CSF samples will be stored for future use for the measurement of exploratory CSF biomarker analyses. Subjects will be analyzed as treated.
- The Randomized population will include all subjects who were randomized. Subjects will be analyzed as randomized.

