# 6.4 Management of Analysis Data

#### 6.4.1 Baseline

Unless otherwise specified, baseline data is defined as the data most recently collected prior to the first dose.

Change from baseline is calculated as:

Change from baseline = post-baseline visit value – baseline value.

If either the baseline or visit value is missing, the change from baseline is set to "missing".

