#### 6.4.3 Missing Data

Unless otherwise specified, there will be no substitutions made to accommodate missing data points.

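### SAP 10.1 labels any confirmed post-dose ADA positive as PMN310-induced without looking at the Day -1 sample, so antibody present before dosing and unchanged afterwards is counted as induced

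*SAP*

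**What the plan says.** SAP 10.1 makes several statements about ADA.

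- *By-visit incidence.* It summarises the "number and percentage of subjects who develop detectable levels of anti-PMN310 antibodies (ADA") by dose level and visit, and says that "ADA status will be treated as categorical data (positive and negative) and summarized descriptively by visit".
- *The induced label.* A separate sentence then classes a subject as "positive for PMN310-induced immunogenicity if the subject has at least one confirmed positive ADA response after dosing".
- *Titre.* Titres are summarised by dose level and visit as observed values. No change or fold-rise from baseline is planned.
- *Cumulative status.* For the optional displays of PK by ADA status, a positive at any time point makes the subject ADA positive throughout. Day -1 is not excluded.
- *Population and listing.* "All immunogenicity analyses will be conducted using the Safety population", and "All immunogenicity data will be presented by timepoint in a by-subject listing".

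Elsewhere, Protocol 6.2.1.1 and SAP Table 1 schedule an ADA sample on Day -1, with post-dose samples on Days 29, 57 and 85 and at the optional Day 120 visit. SAP 6.4.1 gives a general rule that "baseline data is defined as the data most recently collected prior to the first dose", unless otherwise specified. SAP 6.2 states that "The Safety population will include all subjects who receive study drug", which includes placebo subjects. SAP 6.4.3 says, again unless otherwise specified, that "there will be no substitutions made to accommodate missing data points". SAP 6.4.2 does specify otherwise in one respect: an unscheduled result inside the visit window may stand in for a missing scheduled one, and ADA results are on the list of data covered.

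**The concern.** The word *induced* attributes the antibody to the drug. To support that, the rule has to compare post-dose with pre-dose status, and it looks at post-dose samples only. The baseline sample exists and the SAP defines baseline, but 10.1 uses neither for this classification.

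The SAP applies baseline logic in comparable places. Section 8.1 counts an adverse event as treatment-emergent only if it starts or gets worse once dosing has begun. Sections 8.3, 8.4 and 8.6 report change from baseline for laboratory, ECG and vital-sign values.

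ADA incidence is a named exploratory endpoint (SAP 4.2.3). Protocol 9.4.1 lists serum ADA among the safety and tolerability results, and the synopsis says that outcomes of this first-in-human study will inform dose selection in patients. With six PMN310 subjects per cohort, one misclassified subject visibly changes a dose group's rate.

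**Working it through.** The plan states no ADA rate, so there is no figure of its own to reproduce.

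**Step 1. Apply the rules to the possible profiles.** The middle columns compare the SAP 10.1 label with the label under a baseline condition. The last column applies the cumulative any-time-point rule.

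| Profile | SAP 10.1 as written | With a baseline condition | Cumulative status |
|---|---|---|---|
| Day -1 positive, post-dose positive, titre unchanged | Induced | Not induced | Positive |
| Day -1 negative, later positive | Induced | Induced | Positive |
| Day -1 positive, titre rises after dosing | Induced | Boosted, reported separately | Positive |
| Day -1 positive only, negative afterwards | Not induced | Not induced | Positive |
| Never positive | Not induced | Not induced | Negative |

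The first row is the error. The fourth row shows a second inconsistency: a subject positive only before dosing is not induced, yet sits in the ADA-positive group of the PK displays. In addition, nothing in the label sentence restricts it to active treatment, so a placebo subject with a confirmed post-dose positive also meets it literally.

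**Step 2. Effect of one subject.** SAP 6.1 gives 6 PMN310 subjects per cohort in 5 cohorts, the fifth optional.

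- One dose group: 1/6 = 16.7 percentage points.
- All PMN310 subjects with five cohorts: 6 × 5 = 30, and 1/30 = 3.3 points.

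**Step 3. How likely such a subject is.** Let *p* be the share of subjects who are ADA positive before dosing and *s* the share of those who stay positive without a titre rise. Neither is in the documents, so both are assumptions. For a dose group of 6, treating subjects as independent:

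P(at least one) = 1 − (1 − *p·s*)^6

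| Assumed *p* | *s* = 1 | *s* = 0.5 |
|---|---|---|
| 0% | 0% | 0% |
| 2% | 1 − 0.98^6 = 11.4% | 1 − 0.99^6 = 5.9% |
| 5% | 1 − 0.95^6 = 26.5% | 1 − 0.975^6 = 14.1% |
| 10% | 1 − 0.90^6 = 46.9% | 1 − 0.95^6 = 26.5% |

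The expected number per dose group is 6*ps*. With *s* = 1 that is 0, 0.12, 0.30 and 0.60.

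**The case against.** The best defence is that the text leans towards new onset. The incidence sentence speaks of subjects who *develop* antibody, and the label sentence of a *response* after dosing. On that view the rule is only loosely worded, and a sensible programmer would check baseline. This does not hold up. *Develop* is undefined and sits in the by-visit summary. The label sentence is a separate, additional rule with its own complete criterion, and coding it as written uses post-dose results only.

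Other parts of the defence stand.

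- The endpoint is exploratory, SAP 6.6 plans no hypothesis tests, and no pausing rule in SAP 5.3 refers to ADA.
- Day -1 is a scheduled ADA visit, so a baseline positive would show in the by-visit status and titre summaries and in the by-subject listing. That makes the case findable, but it does not correct the label.
- SAP 10.1 defines the classification without specifying a table for it. That it will be reported as a rate per dose group is a reasonable inference from the incidence endpoint, not a stated output.
- Only the 1/6 figure follows from the documents. The probabilities depend on the assumed *p* and *s*.

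A reader might also infer that missing ADA results are left wholly unhandled. The documents do not support that: SAP 6.4.2 lets an in-window unscheduled ADA result replace a missing scheduled one. What stays open is narrower. Section 10.1 does not say how a Safety population subject with no baseline result, or no post-dose result at all, enters the percentage. That is missing detail rather than a wrong rule.

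**Conclusion.** The point holds. As written, the induced label includes a subject whose antibody was present before dosing and did not change. No other section of the protocol or SAP provided adds the missing condition. The count is wrong as labelled whenever such a subject occurs, by 17 percentage points per subject in a six-subject dose group. The chance of at least one in a dose group is 0 to 47% for an assumed pre-existing rate of 0 to 10% with full persistence. If nobody is positive before dosing, the effect of this defect is zero.

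Two stronger readings are not supported. One is that reported incidence in this trial will be inflated: the documents give no pre-existing rate, persistence share or assay cut-point from which to conclude that. The other is that the information is lost: the Day -1 sample is taken and its result is listed. Importance is therefore modest, but the correction is cheap and better made in advance than by sorting subjects after unblinding.

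**What to change.** Amend SAP 10.1 as follows.

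1. **Induced.** Require a negative baseline, taken as the last pre-dose ADA result under SAP 6.4.1, and at least one confirmed post-dose positive. Apply the PMN310-induced label to PMN310-treated subjects only. Run the same derivation for placebo and report it as a background rate.
2. **Baseline positives.** Report them separately. Call them boosted only if the post-dose titre rises over baseline by a fold fixed from assay variability before unblinding. The documents give no such fold, so it has to come from the assay data.
3. **Cumulative status.** For the PK displays, limit the rule to post-dose samples, or show subjects positive only at baseline as a separate group.
4. **Denominator.** Base percentages on Safety population subjects with a baseline result and at least one post-dose ADA result, after the SAP 6.4.2 replacement rule has been applied. Change the sentence that assigns all immunogenicity analyses to the Safety population so that it agrees.

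The cost is SAP wording, a small change to the derived ADA variables and one threshold set from assay data. SAP 3.1 already allows SAP changes approved before database lock, but the fold should be fixed before unblinding. No new samples or visits are needed.
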